2.10.2 Secondary Endpoints

Clinical Endpoints

1. **Study hospital length of stay among survivors to day 90:** Study hospital length of stay is defined as the number of days from enrollment (typically the day of hospital admission) to the day of study hospital discharge up to day 90. This endpoint will be analyzed only in survivors because hospital length of stay in those who die in the hospital is non-informative for this endpoint. In addition, we will use survivor average causal effect (SACE) methods to estimate hospital length of stay among participants that would have survived in both treatment and control groups.⁵⁰ Accordingly, these methods adjust for the impact of differential survival between treatment groups.
2. **Healthcare facility length of stay among survivors to day 90:** Healthcare facility length of stay is the time spent in another hospital or healthcare facility (e.g. long-term acute care [LTAC] hospitals or acute rehabilitation/skilled nursing facility), for the subgroup of participants that were discharged to another healthcare facility after the initial hospitalization. This measure is defined as the number of days from initial hospital discharge to the first facility discharge to home (pre-hospitalization level of care) up to day 90. Healthcare facility LOS is zero for patients discharged to home (pre-hospitalization level of care) from the study hospital. This endpoint will be analyzed only in survivors using SACE methods because healthcare facility length of stay in those who die during the follow-up period is non-informative for this endpoint.
3. **Alive and home at day 90:** This endpoint is the proportion of participants who have survived and are present at home, defined as pre-hospitalization level of care, at day 90.

4. **Ventilator free days (VFD) to day 28:** VFD depends on both duration of ventilation and mortality through study day 28. In participants who survive 28 days, VFD is defined as 28 minus duration of ventilation. Duration of ventilation is counted from the first study day of assisted breathing through the last day of assisted breathing provided the last day is prior to day 28. Otherwise, it is counted from the first study day of assisted breathing through day 28. For participants discharged with assisted ventilation (e.g., to LTAC facility) prior to day 28, a phone call will be required to assess ventilator status at day 28. Participants discharged prior to day 28 (but not to home) on unassisted breathing will be assumed to remain on unassisted breathing through day 28. Isolated periods of ventilation briefer than 24 hours for surgical procedures and ventilation solely for sleep disordered breathing do not count towards duration of ventilation. In participants who never require assisted breathing, duration of ventilation is zero. Participants who do not survive 28 days will be assigned zero VFD. VFD is undefined in participants with chronic/home mechanical ventilation (except solely for sleep disordered breathing) and they will be excluded from this analysis.
5. **Time to mortality to day 90:** Time to mortality will use best available data on vital status and date of death and censor based on last known alive date for participants with missing vital status.

Physiological Endpoints

6. **Development and severity of ARDS to day 7:** We will determine the presence and severity of ARDS for each day of mechanical ventilation to day 7 using the following approach:
 - a. For each ventilator day: if ABG available between 2:00 AM and 8:00 AM, measure P/F (PaO₂, FiO₂ and PEEP) for all ABGs during this time window daily to day 7. Or, for ventilator days that no ABG available between 2:00 AM and 8:00 AM, determine lowest imputed P/F from measured S/F (SpO₂, FiO₂, and PEEP). See Appendix B for P/F imputation table.
 - b. For participants with P/F <300 or imputed P/F <300, FiO₂ ≥40%, and PEEP ≥5 cm H₂O, determine if hypoxemia is valid, acute, and not fully explained by CHF or fluid overload
 - c. If yes to item (b), local investigators will:
 - i. Review the first CXR (or CT) performed on each ventilated day with valid P/F or imputed P/F <300 (to day 7). If no chest imaging studies are present that day, site investigators may review imaging one day before or after to determine if ARDS imaging criteria met.
 - ii. Assess if the images are consistent with ARDS (bilateral opacities not fully explained by effusions, lobar/lung collapse, or nodules). If equivocal, the reviewing investigator will adjudicate with additional investigators.
7. **Change in organ failure severity to day 7:** We will measure acute organ failure severity daily to day 7 for three key organ systems: acute hypoxemic respiratory failure, acute kidney injury, and cardiovascular failure (i.e., shock). We will measure acute hypoxemic respiratory failure using data from the ARDS assessment, except this outcome does not require chest imaging consistent with ARDS. We will measure acute kidney injury by highest daily creatinine values or new use of dialysis/ renal replacement therapy (chronic dialysis

participants are excluded). We will measure cardiovascular failure by highest daily dose of vasopressors (epinephrine, norepinephrine, dopamine, phenylephrine, or vasopressin).

8. **Plasma 25OHD levels:** In addition to the screening vitamin D test (for trial entry), we will measure gold-standard plasma 25OHD levels at baseline for all randomized participants and at day 3 in the first 300 randomized participants to confirm biomarker response to the intervention. The gold-standard test will be done in batch using LC/MS/MS methods. Individual results will not be available to investigators and coordinators to avoid unblinding. Based on pre-specified rules and in consultation with the DSMB (who will have access to additional adverse event data), we may require changes to the vitamin D dose or extend the duration of 25OHD/calcium monitoring.
9. **Plasma IL-6 levels:** We will measure plasma IL-6 levels at baseline and day 3 in the first 300 randomized participants in batch concurrent with 25OHD testing. IL-6 is a pro-inflammatory cytokine associated with increased incidence and severity of ARDS severity and worse clinical outcomes. Vitamin D may improve outcomes in critically ill patients by reducing levels of IL-6 (either causal association or as a result of improved recovery)

Safety Endpoints

10. **Calcium levels to day 14:** Because the half-life of 25OHD is approximately 2 weeks, we will record clinically available serum or ionized calcium levels through day 14 for all randomized participants. In addition, we will measure baseline and day 3 in the first 300 randomized participants in real time, either as part of routine clinical care or as a research procedure if not available. Day 3 is the when 25OHD levels peak in ICU patients given 540,000 IU of vitamin D.^{1,49} While no prior study of acute vitamin D repletion, using similar high doses as our trial, has observed clinically important hypercalcemia, we will confirm these findings in the VIOLET trial. Because little change in calcium levels is anticipated, access to individual-level calcium results will not unblind study staff. During the trial, the DSMB may seek additional subject measurements for safety assessment, though this is not anticipated.
11. **Kidney stones to day 90:** While an association between hypervitaminosis D and kidney stones has been suggested, the relationship with high dose vitamin D supplementation and kidney stones remains controversial. We will assess for incident kidney stones by chart review at the end of the hospitalization and by self-report at the 90 day phone call for those discharged from the hospital prior to day 90.
12. **Fall-related fractures to day 90:** The association between acute vitamin D supplementation and falls/fractures remains unclear. Most data suggest that high dose vitamin D in healthy outpatients may improve muscle function, balance, and bone mineral density, and thus decrease fall-related fractures, but other data suggest that high dose vitamin D supplementation may actually increase the incidence of falls/fractures. Because of this uncertainty and limited data in hospitalized patients, we will assess for incident fall-related fractures by chart review at the end of the hospitalization and by self-report at the 90 day phone call for those discharged from the hospital prior to day 90.

2.11 Subgroups

The primary analysis will be based on randomized participants with baseline 25OHD levels <20 ng/mL by LC/MS/MS (confirmed vitamin D deficient cohort). Secondary analysis will be based on the screened vitamin D deficient cohort (all randomized patients). *A priori* subgroups for analysis will include age, sex, race/ethnicity, residence (independent vs. long-term care facility), BMI, pre-hospitalization vitamin D supplementation, baseline 25OHD level (by the LC/MS/MS method), baseline renal function, ARDS risk factor (e.g., infectious vs non-infectious), LIPS score, pre-randomization mechanical ventilation status, pre-randomization presence of ARDS, and source of ICU admission.

3. Main Manuscript and Statistical Methods

The primary analysis will be based on randomized participants with baseline 25OHD levels <20 ng/mL, as measured by LC/MS/MS (**confirmed vitamin D deficient cohort**). Additional analyses will be based on all randomized participants (**screened vitamin D deficient cohort**).

The main manuscript will include the following tables and figures.

Figure. CONSORT Diagram

Table. Baseline Characteristics (confirmed deficient cohort)

- Demographics
- Co-Morbidities—Charlson, BMI, eGFR, pre-hospital level of care
- VIOLET Risk Factors
- Location—intent to admit, ICU destination
- Illness Severity—SOFA, LIPS, mechanical ventilation, ARDS, vasopressor use, vital signs, WBC, lactate
- Baseline vitamin D (home meds, vitD level by LCMS, calcium level)

Figure. Change in LCMS from Day 0 to Day 3 for (screened deficient cohort)

Summary data in text of results or Supplementary Material

Table. Primary and Main Secondary Endpoints (confirmed deficient cohort)

Primary

- 90 day all-cause, all-location mortality

Secondary Clinical

- Hospital mortality to day 90
- Alive and home (prior level of care) at day 90
- All-cause, all-location 28 day mortality
- Hospital LOS
- Healthcare facility LOS
 - Include proportion that went to healthcare facility (vs home) separately
- VFD to day 28

- Include proportion ventilated to help with interpretation

Secondary Physiological

- Respiratory failure
 - New mechanical ventilation ever to day 7 (Y/N)
 - Lowest P/F in the first 7 days if on mechanical ventilation
- ARDS
 - New ARDS ever to day 7 (Y/N)
 - ARDS severity by Berlin definition at time of new ARDS diagnosis¹
 - Lowest P/F in the first 7 days if ARDS
- AKI to day 7
 - New RRT ever to day 7 (Y/N)
 - Worst AKI severity in first 7 days (no, mild, moderate, or severe AKI by KDIGO criteria²)
 - Highest creatinine in first 7 days
- Cardiovascular failure to day 7
 - New vasopressor use ever to day 7 (Y/N)
 - Highest CV SOFA score in first 7 days
- IL-6 to day 3

Safety

- Calcium to day 14
 - Daily comparison to day 14
 - Hypercalcemia ever during the first 14 days (Y/N)
- Kidney stones to day 90
- Falls to day 90
- Fall-related fractures to day 90
- EQ-5D-5L at day 90 (adjusted for baseline)

Figure. Time to Mortality to Day 90 (confirmed deficient cohort)

Figure. 90-day Mortality by Baseline Vitamin D Level for (screened deficient cohort)

3.1 Statistical Methods for Main Manuscript

All analyses are intention to treat, that is, all randomized participants within each cohort (screened deficient, confirmed deficient) will be included in the analyses specified for each cohort. The confirmed deficient cohort is the primary efficacy cohort per the protocol.

All significance testing will be two-tailed at $\alpha = 0.05$ with no adjustment made for multiple comparisons³

With the exception of the primary outcome, analysis is based on all available data with no imputation of missing data.

The causal clinical effect of treatment on outcomes defined only in patients who are on study is complicated by potential case mix imbalance between the treatment groups due to differential recovery and mortality. However, the proposed statistical methods for these outcomes maintain the correct comparison-wise Type I error rate under the global null of no treatment effect whatsoever on any patient.

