## 7 STATISTICAL CONSIDERATIONS

### 7.1 Statistical Methods Primary Analyses

The primary endpoint is intention to treat all-cause, all-location 90 day mortality in the confirmed vitamin D deficient cohort (LC/MS/MS <20 ng/mL). We will conduct analyses on a modified intention to treat basis (all randomized participants who received either vitamin D formulation or placebo in the confirmed vitamin D deficient cohort).

Sample size is based on a comparison of binomial proportions with an overall one-sided alpha level of 0.025. With 20% mortality rate in the control group and 15% rate in the vitamin D group, three interim looks at the data, and 80% of randomized patients with

Figure 4 Study Flow: analysis plan

[figure not shown]
confirmed vitamin D deficiency by the LC/MS/MS method, the study will have a power of 87.4%. The trial will stop when the screened vitamin D deficient cohort reaches a maximum 3000 randomized participants.

The presumed 20% mortality rate in the control group is based on several recently published clinical trials. In the original Amrein study, mortality prior to discharge home before day 90 was 40% in the control group. Because these participants were enrolled a median 3 days after ICU admission (some lower risk participants were already discharged from the ICU) and European ICUs tend to admit sicker patients than U.S. ICUs (some lower risk ICU patients in the U.S. would be managed in a non-ICU setting in Austria), we anticipate a lower mortality in our trial. In the ProCESS trial, which recruited ED patients early in the course of septic shock, the 90 day mortality was 32%. While similar septic shock patients will be recruited in VIOLET, other eligible patients (in addition to septic shock) will likely have a modestly lower mortality. For example, in the LIPS-A trial, which enrolled ED patients across broader ARDS criteria, the subgroup of patients admitted to the ICU had 11% *in-hospital* mortality (vs. 19% in-hospital mortality in ProCESS). While 90 day mortality was not collected in the LIPS-A trial, we would anticipate a 90 day mortality rate of approximately 18%. However, LIPS-A excluded many potentially eligible patients because of aspirin use, which selected against an older, more chronically ill population. These patients would be included in VIOLET (no aspirin exclusion criteria), which would likely increase the event rate.

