We plan to have three interim analyses at 750, 1500, and 2250 randomized (screened vitamin D deficient) participants. In addition, there will be an initial evaluation specifically of 25OHD and calcium levels after the first 300 randomized participants to confirm that the intervention repletes vitamin D deficiency without hypervitaminosis D or clinically significant hypercalcemia, consistent with prior trials using the same dose in ICU patients. DSMB meetings will occur as close to these planned analyses as scheduling allows. The study will be stopped for efficacy based on an analysis of the confirmed vitamin D deficient (LC/MS<20 ng/mL) participants. There will be an efficacy stopping rule at each interim analysis based on a the Lan-DeMets alpha spending function of  $0.025t^4$ , where  $t$  is the proportion of the sample size that has accrued.

In addition, Berry Consultants developed the futility stopping rules for this study according to the following specification. The study will continue until there are 3000 patients randomized, unless it stops early for efficacy or futility. The futility stopping rules will be based on the death rates in each treatment and the proportion of randomized participants who have LC/MS/MS level <20 ng/mL (ie, the inclusion rate). The rule will calculate the predictive probability that the trial will reach statistical significance, when 3000 total randomized participants are enrolled. The futility rules will not be binding on the DSMB, as they will have other information on the secondary analyses of the study as well as information from outside the study. The following table gives the power of the study under different scenarios under the assumption that 80% of the randomized participants will have a LC/MS/MS level <20 ng/mL. The plot below shows individual simulated trials with colors indicating whether they were positive and whether they were stopped early for futility.

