### Futility Stopping Boundaries

Control Rate	Effect	Power	Success (N=750)	Success (N<=1500)	Success (N<=2250)	Futility (N=750)	Futility (N<=1500)	Futility (N<=2250)	E[N]	E[n]
0.1	0.02	0	0	0	0	0.742	0.963	0.998	973	778
	0	0.02	0	0	0.005	0.467	0.728	0.892	1431	1145
	-0.01	0.106	0.001	0.009	0.044	0.328	0.545	0.72	1785	1412
	-0.02	0.356	0.002	0.043	0.18	0.177	0.295	0.421	2176	1741
	-0.03	0.685	0.006	0.13	0.422	0.076	0.135	0.192	2279	1824
0.15	-0.04	0.918	0.017	0.333	0.743	0.033	0.043	0.054	2083	1666
	-0.05	0.985	0.068	0.649	0.951	0.007	0.009	0.01	1730	1384
	0.02	0	0	0	0	0.703	0.933	0.986	1034	827
	0	0.033	0	0.005	0.018	0.442	0.724	0.877	1450	1160
	-0.01	0.099	0.001	0.005	0.031	0.317	0.539	0.727	1785	1428
0.2	-0.02	0.289	0.003	0.027	0.121	0.18	0.329	0.484	2142	1714
	-0.03	0.524	0.003	0.069	0.291	0.13	0.207	0.292	2256	1805
	-0.04	0.758	0.007	0.167	0.524	0.069	0.116	0.149	2226	1781
	-0.05	0.934	0.031	0.36	0.777	0.029	0.041	0.051	2033	1626
	0.02	0.001	0	0.001	0.001	0.704	0.935	0.991	1026	821
0.2	0	0.023	0	0	0.007	0.473	0.74	0.89	1418	1134
	-0.01	0.095	0.002	0.006	0.034	0.341	0.567	0.738	1734	1387
	-0.02	0.228	0.002	0.025	0.099	0.236	0.395	0.545	2024	1619
	-0.03	0.44	0	0.049	0.216	0.144	0.271	0.377	2207	1766
	-0.04	0.661	0.004	0.123	0.41	0.095	0.138	0.201	2272	1816
-0.05	0.874	0.016	0.244	0.637	0.035	0.06	0.08	2196	1757	

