2.9 Sample Size/Interim Monitoring

1. We base our assumptions on finding a 5% or greater absolute difference in mortality. With a 20% mortality rate in the control arm and a 15% mortality rate in the intervention arm, the maximum required total sample size is 3000 randomized participants with 87.4% power based on the assumption that 80% of the randomized participants will have baseline 25OHD levels < 20 ng/mL, as measured by LC/MS/MS, and one sided $\alpha = 0.025$.
2. The principal analysis will be based on randomized participants with baseline 25OHD levels <20 ng/mL, as measured by LC/MS/MS (confirmed vitamin D deficient cohort), following an intention-to-treat principle (analysis according to randomization assignment). We anticipate that approximately 80% of randomized participants will have baseline 25OHD levels <20 ng/mL by LC/MS/MS. The maximum size of the screened vitamin D deficient cohort will be 3000 patients and the futility stopping boundaries will consider the possibility that the sample size will not reach 2400 (80% of 3,000) in the confirmed vitamin D deficient cohort if too small a fraction of randomized patients would have baseline 25OHD levels <20 ng/mL by LC/MS/MS.
3. An independent Data and Safety Monitoring Board (DSMB) will determine if the study should stop for superiority or futility of the intervention, or safety concerns. There will be three interim analyses throughout the trial (at subject enrollments 750, 1500, and 2250 randomized participants).
4. For the first 300 randomized participants, we will analyze calcium levels at baseline and day 3 and 25OHD levels at day 3 using LC/MS/MS. This analysis will evaluate the

effectiveness and safety of the vitamin D intervention in correcting vitamin D deficiency (clinical outcomes will not be evaluated at this time). Based on pre-specified rules and in consultation with the DSMB (who will have access to additional adverse event data), we may require changes to the vitamin D dose or extend the duration of 25OHD/calcium monitoring.

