3.2 Primary Endpoint

The primary outcome of all-cause, all-location mortality to day 90 will be compared between treatment groups on the risk difference scale using a generalized linear model with a binomial distribution function and identity link function. This is equivalent to a Z-test comparing the difference between two proportions but extends naturally to assessment of sub-group by treatment interactions on the risk difference scale.

For participants that have missing 90-day mortality, we will use the Centers for Disease Control and Prevention's National Death Index (NDI) to determine vital status, using each patient's social security number (SSN) for an exact NDI match or other identifying information if SSN unavailable. If none of the patients with missing 90-day mortality are found in the NDI to have died within 90 days we will assume they are all alive at 90 days. If any are known to be deceased, we will impute 90-day mortality for the remaining patients with unknown status using a multi-state model to estimate the transition probabilities across recorded states (in hospital, post hospital facility, home, death). In addition, we will include a sensitivity analysis based on the assumption that the probability of death increases with elapsed time since last follow up.

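### The SAP's flat two-tailed 0.05 leaves no room for alpha spent at three efficacy looks: a final critical value of 1.96 gives one-sided error 0.0270, not 0.025

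*SAP*

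**What the plan says.** Protocol 7.1 fixes the overall error rate: "Sample size is based on a comparison of binomial proportions with an overall one-sided alpha level of 0.025". It plans looks at 750, 1500 and 2250 of 3000 randomized participants. Its efficacy rule spends 0.025t^4, with t the fraction of the planned sample accrued so far. The sentence that sets this rule begins "There will be an efficacy stopping rule at each interim analysis based on a the Lan-DeMets alpha spending function of". On futility it says "The futility rules will not be binding on the DSMB".

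SAP 2.9 repeats the one-sided 0.025 and the three looks, but neither that section nor any other in the SAP mentions the spending function. SAP 3.1 sets the significance level for the main manuscript: "All significance testing will be two-tailed at $\alpha = 0.05$ with no adjustment made for multiple comparisons". SAP 3.2 describes the primary test, "The primary outcome of all-cause, all-location mortality to day 90 will be compared between treatment groups on the risk difference scale", with a binomial identity-link model that it equates to a Z-test for two proportions. It states no critical value. Neither document prints a numerical efficacy boundary for any look.

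**The concern.** A spending function that reaches 0.025 only at t = 1 leaves the final look just the part not already spent. An analyst who follows SAP 3.1 and 3.2 as written would compare the final Z with 1.96, as if no earlier efficacy looks had been made. SAP 3.1 does exempt the primary outcome from its missing-data rule, so the lack of an exemption from the significance level is conspicuous.

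The sentence can also be read as concerning multiplicity across outcomes only. The SAP is then silent on the threshold for the primary test. Under either reading, the threshold for the mortality claim could be left to be settled after the data are seen.

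**Working it through.** **Inputs.** Overall one-sided alpha 0.025, spending 0.025t^4, and looks at 750, 1500 and 2250 of 3000, so t = 0.25, 0.50, 0.75, 1 (Protocol 7.1; Appendix D gives approximately 25%, 50% and 75%). Allocation is 1:1 (Protocol 4.3.1). The primary cohort is 80% of 3000 = 2400, or 1200 per arm; mortality is 20% v 15% (Protocol 7.1, SAP 2.9).

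**Reproducing the plan's own figures.** The standardised effect at full size is 0.05 / √(0.20×0.80/1200 + 0.15×0.85/1200) = 3.230.

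- A fixed design has power Φ(3.230 − 1.960) = 89.8%.
- With the 0.025t^4 boundaries and no futility stopping, power is 89.4%.
- With futility cut-offs calibrated to the protocol's futility rates it is 85.5% to 86.2%, within 2 points of the stated 87.4%.
- Without futility, cumulative success at the three looks is 0.017, 0.249 and 0.644. The row for 20% control mortality and a 5-point reduction, in the protocol table headed "Futility Stopping Boundaries", shows 0.016, 0.244 and 0.637. The boundaries derived below are therefore close to those behind the protocol's table.

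**Boundaries.** Under the null, Z at looks i < j has correlation √(t_i/t_j). Each boundary c_k solves P(no earlier crossing, Z_k ≥ c_k) = 0.025(t_k^4 − t_(k−1)^4).

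| t | Cumulative alpha, 0.025t^4 | Boundary z |
|---|---|---|
| 0.25 | 0.0001 | 3.725 |
| 0.50 | 0.0016 | 2.967 |
| 0.75 | 0.0079 | 2.442 |
| 1.00 | 0.0250 | 1.998 |

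The final 1.998 is one-sided 0.0228, or two-sided 0.0457.

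**Using 1.96 at the end.** Looks 1 to 3 spend 0.00791. The final look at 1.96 adds 0.01908. The total is 0.00791 + 0.01908 = 0.02699. Multivariate-normal integration gives the same value. Simulating 2 million binary trials at 20% mortality in both arms gives 0.0269 with a pooled variance and 0.0273 unpooled; with 1.998 the figures are 0.0249 and 0.0253.

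**Look timing.** Protocol 7.1 says "DSMB meetings will occur as close to these planned analyses as scheduling allows", so the fractions may move. The shifts below are assumed.

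| Interim looks at (%) | Final z | Two-sided p | Error with 1.96 |
|---|---|---|---|
| 20, 45, 70 | 1.990 | 0.0466 | 0.0266 |
| 25, 50, 75 | 1.998 | 0.0457 | 0.0270 |
| 30, 55, 80 | 2.009 | 0.0446 | 0.0274 |
| 25, 50, 90 | 2.031 | 0.0422 | 0.0280 |

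**If futility stopping were always obeyed.** The documents give no numerical futility threshold, so these rules are assumed. Z cut-offs of −0.07, 0.53 and 1.09 reproduce the protocol's null row at 20% mortality (0.473, 0.74, 0.89). With them the error is 0.0233 with 1.96 and 0.0218 with 1.998. Predictive-probability cut-offs of 10% and 5% give 0.0237 and 0.0254 with 1.96. The protocol's simulated null rows (0.020, 0.033, 0.023) vary by far more than 0.0233 − 0.0218 = 0.0015, so they do not show which final value was used.

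**On the data scale.** At 1200 per arm and 20% observed control mortality, the difference needed moves from 3.10 to 3.16 points. In deaths that is 0.0310×1200 = 37.2 against 0.0316×1200 = 37.9, less than one death.

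**The case against.** The strongest reply is that the protocol already settles the matter. An overall one-sided 0.025 with 0.025t^4 determines the final boundary once the information fractions are known, and a Lan-DeMets design normally leaves the number unprinted for that reason. The SAP 3.1 sentence ends on multiple comparisons and cites a multiplicity paper, so its natural subject may be the many outcomes. On that view 0.0270 follows from only one reading. This stands in part: the SAP does not expressly order 1.96 for the final primary test. But its rule covers all testing, nothing in SAP 3.2 overrides it, and the method that would is absent from the SAP.

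The effect is also small. The disputed band, z from 1.960 to 1.998, has probability 0.0270 − 0.0250 = 0.002 under the null. For any true effect it cannot exceed about 0.038×0.399 = 1.5%. If futility stopping is obeyed, the error with 1.96 is about 0.023 to 0.025. These figures are right and limit the importance of the point. They do not supply type I error control, because the futility rule is not binding.

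Two further points have some force. The DSMB charter mentioned in Protocol Appendix D is not among the documents and may record boundaries; the final-analysis threshold belongs in the SAP in any case. And the spending function concerns efficacy only, so a bare two-sided 0.0457 would also tighten the test for harm. The boundary is better stated as one-sided, in favour of vitamin D.

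**Conclusion.** The concern holds. Followed literally, SAP 3.1 conflicts with the protocol's error control. Read narrowly, the SAP leaves the final threshold for the primary test unstated. With looks at the planned fractions and no credit for futility, a final 1.96 gives a cumulative one-sided error of 0.0270 against 0.025; it is 0.0266 to 0.0274 if all looks fall 5 points early or late. The conclusion would differ only if the trial reaches the final look with a two-sided p between about 0.0457 and 0.05 in favour of vitamin D. The SAP as written would then declare success when the protocol's spending function is not satisfied. This should be fixed because it is the decision rule for the primary claim, although the numerical excess is slight.

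**What to change.** In SAP 3.1, limit the flat two-tailed 0.05 to analyses other than the primary test. In SAP 3.2, state that the primary endpoint is tested at the final look against the efficacy boundary from the Lan-DeMets function 0.025t^4 (overall one-sided 0.025), recomputed from the information fractions actually used at the interim looks. Give the planned-fraction value as an illustration: z = 1.998 in favour of vitamin D, one-sided 0.0228, equivalent to two-sided p < 0.0457.

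The cost is wording only; no cohort, estimate or test statistic changes. At 20% v 15%, power before futility is 89.4% with the boundary against 90.1% with 1.96, a loss of about 0.6 points before rounding (0.9007 − 0.8943). It is about 0.5 points if the assumed futility cut-offs are always obeyed.
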